Photography: Close-up photographs of the subject's target great toenail will be used for documentation purposes only and will not be used for determinations of eligibility or any study-related activities.

Statistical Methods:**Safety:**

All subjects who receive at least 1 confirmed dose of study drug will be included in the safety analysis set. No imputations will be made for missing safety data. The primary safety objective will be considered met when approximately 40 evaluable subjects have been treated for 48 weeks.

All AEs occurring during the study will be recorded and classified using the Medical Dictionary for Regulatory Activities (MedDRA). Treatment-emergent adverse events (TEAEs) are those AEs with an onset on or after the date of first study drug application. All TEAEs will be summarized by the number of subjects reporting each TEAE, the associated system organ class and preferred term, the severity, and the relationship to study drug for the Safety, PK and Non-PK populations. Each subject will be counted only once within a system organ class or a preferred term using the event with the greatest severity or causality, respectively, within each category.

Serious adverse events (SAEs) will be summarized by the number of subjects reporting each SAE, the associated system organ class and preferred term, the severity, and the relationship to study drug for the Safety, PK and Non-PK populations.

Local skin reaction scores (redness, swelling, burning, itching, and vesication) at each study visit will be summarized using frequency tables for the Safety, PK and Non-PK populations. Additionally, redness and swelling severity scores will be summarized using descriptive statistics (mean, standard deviation [SD], median, and minimum and maximum). Subjects with a severity score worse than baseline will also be summarized at each postbaseline study visit. The worst score and the last score during the post-baseline period will also be summarized.

Results of safety laboratory parameters and vital sign measurements will be summarized at each study visit using descriptive statistics or frequencies and percentages, as appropriate, for the Safety, PK and Non-PK populations. Changes from baseline in safety laboratory values will be summarized by treatment group at Week 48 using descriptive statistics. In addition, changes from baseline in safety laboratory values will be summarized using shift tables according to normal ranges.

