This study's primary object is to assess the safety of the study drug. Descriptive efficacy statistics for the endpoints will assist in evaluating compliance with treatment for the purposes of safety assessment.

The efficacy endpoints include the following:

- Complete Cure, defined as 0% clinical involvement of the target toenail and negative KOH and fungal culture at Week 52
- Complete or Almost Complete Cure at Week 52, defined as :: 5% toenail involvement
- Clinical Efficacy rate at Week 52, defined as an affected target great toenail area of <10%
- Mycologic Cure rate at Week 52, defined as a negative KOH examination and a negative fungal culture of the target great toenail sample

The Complete Cure rate, the Complete or Almost Complete Cure rate, the Clinical Efficacy rate, and the Mycologic Cure rate will be presented using descriptive statistics (sample size n, frequency counts and percentages) for the Safety, PK and Non-PK populations. In addition, the growth of the target great toenail at each study visit and the change from baseline in the number of affected nontarget toenails will be descriptively summarized.

A last observation carried forward (LOCF) imputation will be used to impute missing values for the efficacy variables at Week 52. No sensitivity analyses will be conducted.

Any subjects remaining (i.e., have not been treated for 48 weeks) will be followed until completion. The final report will be amended with data on these subjects.

Pharmacokinetics:

All subjects in the PK subset who receive at least 1 confirmed dose of study drug and have any PK data on Days 28 and 29 will be included in the PK analysis set. Blood samples will be tested for plasma concentrations of efinaconazole and metabolites (H3 and H4). No imputations will be made for missing data. Plasma concentrations that are reported as below the limit of quantitation (BLQ) in the data transfer file will

be set to zero for the summaries of concentrations as well as calculation of PK parameters. Missing values will be treated as if they were never drawn. Plasma concentrations of efinaconazole and metabolite (H3 and H4) and PK parameters will be summarized using descriptive statistics (n, mean, SD, standard error of the mean [SEM], coefficient of variation [CV], median, minimum, and maximum). Geometric means will also be used to summarize C_{max} , C_{min} , $AUC_{(0-t)}$ and $AUC_{(0-24h)}$.

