11.1.1 Screening Visit (Visit 1, Up to Day -42)

After signing the informed consent/assent, subjects will undergo the screening procedures to confirm eligibility to participate in the study.

Newly screened PK subjects will decide at the time of signing consent whether they will consent to the 4-Week trial or participate in the 52-Week trial.

Note: *Subjects that consent to 4 -Week trial will not be allowed to extend their study consent to 52 weeks. Subsequently, PK subjects who consent to the 52-Week trial will be considered discontinued/Early Terminated if he/she discontinues prior to the Week 52 visit.*

The following procedures will be conducted at this visit:

1. Review and explain the nature of the study. Provide a visit schedule with the length of each visit to ensure that the subject can meet the requirements and has adequate transportation.
2. Obtain verbal and written informed consent/assent from the subject and the subject's parent(s) or legal guardian(s) prior to performing any study-related procedures. Provide signed copies of the consent and assent forms to the subject/parent(s) or legal guardian(s).
3. Obtain photography consent/assent from subject and/or the subject's parent(s) or legal guardian(s).
4. Assign a 6-digit study number, which includes the 3-digit investigational center number plus a unique 3-digit subject number beginning with 001 (eg, 001-001, 001-002, 001-003). Numbers must be assigned in chronological order.
5. Record subject's demographic information (sex, date of birth, age, ethnicity, and race).
6. Record subject's medical history including diabetes history.
7. Collect a detailed history of onychomycosis, including an estimated start date of infection, duration of current infection in the potential target great toenail, and all previous therapies used for onychomycosis treatment.
8. Review all prior medications (those used within 30 days prior to the Screening Visit) and previous antifungal medications used by the subject, including any recent over-the-counter topical treatments (those used within 60 days prior to the Screening Visit).
9. Review inclusion/exclusion criteria.

10. Examination of toenails for clinical presence of onychomycosis in at least 1 great toenail, within the definition of eligibility criteria. For subjects in the PK population, both great toenails and 4 other toenails must meet eligibility criteria
11. Examination of all other toenails for presence or absence of onychomycosis on each toenail.

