Note: PK subjects exiting the study on Day 29 (consented to only the 4-Week trial), the following procedures will be conducted in addition to the procedures listed above.

11. Collect blood and urine samples for routine safety laboratory analysis (hematology, serum chemistry, and urinalysis). Process and ship the samples to the central safety laboratory per instructions provided in the laboratory manual.
12. Measure height and weight.
13. Conduct an abbreviated physical examination (excluding urogenital/reproductive systems).

For subjects in the PK subset at Visit 3 only:

- Collect a predose blood sample after all other study procedures are completed.
- Apply the study drug to all 10 toenails at the investigational center within 1 hour after collecting the predose blood sample.
- Collect postdose blood samples at approximately 2 hours (\pm 5 min), 4 hours (\pm 5 min), and 12 hours (\pm 15 min) after study drug application.
- Instruct the subject to return the following morning for their 24-hour blood sample (Visit 3A (Day 29). Subject will not dose on the evening of Day 28.

11.1.4 Visit 3A (Week 4, Day 29) - Additional Visit for Subjects in the PK Subset

The following procedures will be conducted at this visit:

1. Record any AEs (query subject "Are there any changes in your health?").
2. Record local skin reaction scores reported by the subject.
3. Review concomitant medications.
4. Collect a blood sample 24 hours (\pm 30 min) after study drug application at Visit 3.
5. Obtain 1 bottle of study drug and weigh the bottle, complete the label and drug log, and dispense the bottle to the subject and their parent/legal guardian. Review the new dosing instructions with the subject (application to only the target great toenail and to any other affected toenails) and provide a copy of new dosing instructions to the subject.
6. Dispense a new diary that includes the new dosing instructions.

Note: PK subjects who consented to only the 4 Week trial will exit the study on Day 29. Drug and subject diary will not be dispensed and urine pregnancy test will not be collected at this visit.

11.1.5 Schedule the PK subset subject (if consented to the 52-Week trial) for the next study visit. Visit 5 (Week 12 [\pm 5 days]), Visit S (Week 24 [\pm 5 days]), Visit 11 (Week 36 [\pm 5 days])

Visits are to be scheduled in reference to Visit 2 (Baseline).

The following procedures will be conducted at these visits:

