11.1.10 Subject Completion

A subject has completed the study when Visit 15 (Week 52) has been completed and the subject has been exited from the study. Subjects who require further follow-up for an AE following completion of the study will be followed according to Section 12.0.

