12.3 Subject Disposition

Subject disposition will be summarized for each analysis population.

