12.7 Interim Analyses

An interim analysis will be performed to summarize available safety data at a predefined date to be determined by the sponsor. It will be performed for all available data on the PK and non-PK portion of the study. This interim analysis will contain all tables and all listings just like the final analysis, using the locked data for the interim analysis.

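### Does the new Day 29 exit for 4-week PK subjects leave the 48-week target and the completion rule unworkable?

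*Combined protocol and SAP*

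**What the plan says.** All references are to the current amendment, which introduced the two consent options for the PK subset.

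- **Exit.** Section 11.1.4: "PK subjects who consented to only the 4 Week trial will exit the study on Day 29". Under Section 11.1.1 these subjects "will not be allowed to extend their study consent to 52 weeks".
- **Status.** The same note in Section 11.1.1 adds: "PK subjects who consent to the 52-Week trial will be considered discontinued/Early Terminated if he/she discontinues prior to the Week 52 visit". It gives no matching statement for 4-week subjects.
- **Completion.** Section 11.1.10: "A subject has completed the study when Visit 15 (Week 52) has been completed and the subject has been exited from the study".
- **Target.** Synopsis, Statistical Methods, Safety: "The primary safety objective will be considered met when approximately 40 evaluable subjects have been treated for 48 weeks".
- **Follow-up.** Synopsis, Statistical Methods: "Any subjects remaining (i.e., have not been treated for 48 weeks) will be followed until completion". The final report is then amended with their data.
- **Disposition.** Section 12.3: "Subject disposition will be summarized for each analysis population".
- **Interim.** Section 12.7: "An interim analysis will be performed to summarize available safety data at a predefined date to be determined by the sponsor".

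Section 12.8.2 plans about 60 subjects, about 20 of them in the PK subset, and states that there was no formal sample size calculation. Section 12.8 rules out hypothesis tests.

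**The concern.** The amendment shortened the study for some PK subjects, but three rules written for a 48-week course stayed as they were.

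1. A 4-week subject can never reach Visit 15, so never meets the only completion definition. If the disposition table took its completer category from Section 11.1.10 alone, planned exits would sit with true losses.
2. Read literally, the follow-up sentence covers anyone treated for less than 48 weeks. That includes 4-week subjects, who have left and may not extend.
3. The target of about 40 does not say whether PK subjects on the 52-week option count, and *evaluable* is not defined in the protocol. The planned non-PK group equals the target exactly, so who counts seems to decide whether there is any room for loss.

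In addition, the Synopsis describes a report followed by an amended report, while Section 12.7 describes an interim analysis followed by a final one.

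**Working it through.** **Status of a Day 29 exit.** Four places bear on it besides Section 11.1.10:

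- Table 1 has a scheduled study-exit mark at the Week 4 stage, with footnote t limiting it to 4-week PK subjects.
- Footnote b limits the Early Termination procedures to non-PK subjects and PK subjects on the 52-week trial.
- Section 11.1.1 applies the discontinued label only to 52-week PK subjects.
- Section 11.1.6 has the site record a reason for discontinuation at the Early Termination Visit, which a 4-week subject leaving on schedule does not have.

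Together these make the exit planned. Section 12.3 does not tie its categories to Section 11.1.10. The consent option is fixed at screening, so a table can separate the two groups from data already held.

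**Subjects remaining.** A subject who has exited is not ordinarily still remaining. The strict reading would also catch every early discontinuer, and the same sentence stood in the versions before the 4-week option existed. The amendment did not create that difficulty.

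**The target.** Inputs are 60 in total and 20 PK (Section 12.8.2), and 40 (Synopsis). The plan's own split is reproduced: 60 − 20 = 40 non-PK subjects. Let m be the number of PK subjects on 4 weeks. The documents do not give m, so the full range is shown.

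If everyone planned for 48 weeks counts, the pool is 60 − m, the allowance is 20 − m, and its share is (20 − m)/(60 − m). Apparent non-completion with no true loss, under Section 11.1.10 alone, is m/60 overall and m/20 in the PK subset.

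| m | Pool | Allowance | Share | m/60 | m/20 |
|---|---|---|---|---|---|
| 0 | 60 | 20 | 33.3% | 0% | 0% |
| 5 | 55 | 15 | 27.3% | 8.3% | 25% |
| 10 | 50 | 10 | 20.0% | 16.7% | 50% |
| 15 | 45 | 5 | 11.1% | 25% | 75% |
| 20 | 40 | 0 | 0% | 33.3% | 100% |

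Three conditions limit what this table shows.

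- The allowance columns assume that 52-week PK subjects count. If only non-PK subjects count, the allowance is 40 − 40 = 0 for every m, including m = 0, so the amendment changes nothing.
- m = 20 requires that no PK subject enrolled before the amendment and that every later one chose 4 weeks. Section 11.1.1 offers the choice to newly screened PK subjects only.
- The last two columns require a disposition table that ignores Table 1 and Section 11.1.1.

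**What a shortfall would cost.** The documents give no loss rate. Assume 10% to 20% in the worst-case pool of 40: 36 to 32 would be expected to reach Week 48, and the exact binomial chance of at least 40 is 0.015 at 10% and below 0.001 at 20%. That sounds severe, but the target is approximate and triggers no test. In terms of information, with no event observed the one-sided 95% upper bound on an event rate is 1 − 0.05^(1/n): 7.2% at n = 40, 8.0% at n = 36 and 8.9% at n = 32. The loss of precision is modest. Subjects who leave early also stay in the safety population with the data they gave.

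**Reporting sequence.** The summary of changes says that the former data-cut plan in Section 12.8 was replaced by Section 12.7. The Synopsis sentence on amending the final report belongs to the older plan. Under either sequence data are reported once early and again at the end, and the analysis is descriptive, so no error rate depends on the order.

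**The case for a change.** The best case for a change is that the sponsor plainly meant to carry the Day 29 exit through the protocol. The laboratory tests, vital signs, physical examination, schedule and early-termination footnote were all updated, and these rules were missed. Sections 11.1.4 and 11.1.10 do not fit together whatever the SAP says. Many PK subjects may have chosen 4 weeks, and a reader of the disposition table should be able to tell planned exits from losses. The repair would take three sentences and a split in one table.

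Much of this stands. Section 11.1.10 lacks a line for the 4-week option, and the amended-report sentence in the Synopsis was not reconciled with Section 12.7. What does not stand is the consequence. No passage says that planned exits will be reported as losses, and several point the other way. No passage calls the 20 PK subjects a reserve for the 40; Section 12.8.2 rests the sizes on PK and clinical grounds. Nor is the question of who counts wide open. Treatment for 48 weeks excludes 4-week subjects and, on its face, includes PK subjects who complete the longer course.

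**Conclusion.** This is missing detail together with a clerical leftover, and no change to the plan is needed. An analyst with Table 1, Section 11.1.1 and Section 11.1.4 would label a 4-week subject who finishes Visit 3A as having completed the 4-week option, and would apply the follow-up sentence only to subjects still on the 48-week course. Writing this down would not alter the safety population, the adverse event tables, the PK analysis or the target of about 40. The effect is limited to the label given to m subjects in a descriptive table, with m somewhere from 0 to about 20.

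The conclusion rests on two assumptions: that each PK subject's consent option is held in the data, which follows from its being decided at screening, and that disposition is read together with the early-termination rules. Section 12.8 calls the SAP a separate document. None of its text was available for this check, so *evaluable* may be defined there.

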Onychomycosis is a chronic and recurring fungal infection of the fingernails or toenails that accounts for about half of all nail disorders. Onychomycosis is usually caused by dermatophytes, either *Trichophyton rubrum* (71%) or *Trichophyton mentagrophytes* (20%). The prevalence of onychomycosis in the United States (US) may be as large as 13%, with the infection observed predominantly in elderly patients (60%) [1, 2]. Onychomycosis of the toenail can result in permanent toenail deformity and has a significant impact on quality of life due to concerns with the appearance of the toenails and interference with wearing shoes, walking, and participating in various sports activities [3, 4].

Cure rates for topical treatments have been significantly lower than currently available systemic medications [5], presumably because they bind strongly to keratin and do not adequately penetrate the nail unit. However, while effective, oral therapy is limited by safety concerns due to systemic exposure. For example, both oral itraconazole and oral terbinafine have the potential to cause drug-drug interactions and hepatotoxicity. Efinaconazole 10% Solution (efinaconazole) has a low affinity for keratin binding and has a higher binding reversibility than that of other reference drugs. Therefore, efinaconazole appears to be a promising antifungal compound for the topical treatment of onychomycosis.

Efinaconazole is a novel triazole antifungal agent that is active in vitro against a wide range of pathogenic fungi and is expected to be effective in the treatment of mild to moderate onychomycosis.

Efinaconazole has been shown to be efficacious in vitro against a panel of fungal species that invade human skin, hair, and nails including dermatophytes *Trichophyton*, *Microsporum*, *Epidermophyton*, and the yeast, *Malassezia* species, responsible for *tinea unguium* (onychomycosis), *tinea corporis*, *tinea pedis*, *tinea capitis*, and *pityriasis versicolor*.

Efinaconazole has been shown to be fungicidal against *Candida albicans* and other *Candida* species responsible for the major yeast (nondermatophyte) form of onychomycosis and cutaneous candidiasis. In vitro studies against dermatophytes showed that efinaconazole was more potent than clotrimazole, but less potent than butenafine.

Efinaconazole has successfully treated experimentally induced dermal candidiasis, *tinea corporis*, *tinea pedis*, and *tinea unguium* in vivo in guinea pig models. It has generally out performed reference drugs in these models, and in particular out performed the marketed drugs for *tinea unguium*: ciclopirox olamine (approved for the topical treatment of onychomycosis in the US), amorolfine (available outside the US as a topical nail lacquer), and terbinafine (available in the US in oral form).

The safety and efficacy of once daily use of efinaconazole for the treatment of onychomycosis of the toenail were assessed in two 52-week prospective, multicenter, randomized, double-blind

clinical studies. These studies were conducted in subjects 18 to 70 years of age with 20% to 50% clinical involvement of the target great toenail, without dermatophytomas or lunula (matrix) involvement (n = 870 in Study 1 and n = 781 in Study 2) [6]. These studies evaluated 48-weeks of treatment with efinaconazole relative to vehicle solution. At Week 52 (4-weeks after completion of therapy), efinaconazole was superior to vehicle solution in both studies and thus demonstrated efficacy in the treatment of onychomycosis. The most common adverse reactions (ie, reactions with incidences > 1%) reported in the studies were ingrown toenails, application site dermatitis, application site vesicles, and application site pain.

Efinaconazole was approved by the US Food and Drug Administration in June 2014 for the topical treatment of onychomycosis of the toenail(s) due to *T rubrum* and *T mentagrophytes* (Jublia® [efinaconazole] topical solution, 10% [6]). The approved drug is intended for topical application to affected toenails once daily for 48 weeks. During application, the toenail, toenail folds, toenail bed, hyponychium, and undersurface of the toenail plate are to be completely covered.

The current clinical study is designed to evaluate the safety and pharmacokinetics (PK) of once daily topical application of efinaconazole in the treatment of pediatric subjects with mild to severe onychomycosis of the toenails. Application and use of the study drug is consistent with the approved package insert. The evaluations included in the current study are consistent with the evaluations conducted in the development of the approved drug.

6 Study Objectives and Purpose

The primary objectives of this study are to evaluate: 1) safety of once daily topically administered efinaconazole 10% for 48 weeks in pediatric subjects (6-16 years, 11 months of age) with at least mild onychomycosis of the toenails, and 2) pharmacokinetics PK (4 weeks) of once daily topically administered efinaconazole 10% in pediatric subjects (12-16 years, 11 months of age) with moderate to severe onychomycosis of the toenails.

7 Investigational Plan

